Patients will be evaluated at 6, 12, 18, and 24 study months (\pm 2 months) for repeat swabs (1. one swab of both nares; 2. one swab of the throat; 3. one swab of the bilateral groin areas; 4. one swab of the axilla areas; and 5. one swab of the perirectal area). Patients will also complete questionnaires regarding recent antibiotic use, recent soft tissue infections, recent sexually transmitted diseases, hospitalizations, substance use, sexual activities, and activities previously associated with MRSA (refer to case report forms). Study coordinators will search the patient's medical records and the hospital computer database for medication use, medical conditions including MRSA or soft tissue infections, hospitalizations, sexually transmitted diseases, and HIV data including CD4 count, viral loads, and CDC staging.

Culture results regarding MRSA carriage are to be finalized within 3-4 days of collection. Patients found to have a positive culture for MRSA during the study period from the colonization swabs will be randomized in a 1:1 double-blinded fashion to mupirocin (Bactroban®) nasal ointment twice daily for seven days plus hexachlorophene (pHisoHex®) washes with showering once daily for seven days or to a placebo nasal ointment (white petroleum) and a placebo body soap with no antimicrobial activity for seven days. The patient will be randomized within 7 days of the receipt of the MRSA positive culture result. Women of childbearing age will have a urine pregnancy test to assure they are not pregnant before dispensing of these medications; women found to have a positive pregnancy will be terminated from the study.

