Patients who are colonized with MRSA and who reside locally to the medical treatment facility and are able to return to the clinic will have repeat swabs (five swabs from sites listed above) every month (+/- 7 days). A month will be specifically defined as 28 days. Those who have repeat positive colonization swabs during this initial 6 month follow-up period will be observed. This data will assess the efficacy of decolonization procedures on MRSA carriage rates. Patients who are not local to the clinic will not have these repeat swabs performed, but rather will be seen at the next scheduled 6 month study visit. Adherence to the study medications will be assessed at the next scheduled study visit by a patient questionnaire (refer to case report forms). Each time a patient has a positive isolate for MRSA or MSSA, this will be frozen and saved for molecular analysis to determine the most common molecular types colonizing HIV patients and to determine if patients acquire new strains or remain colonized with the same strain over time.

All study patients (both those initially found to be colonized with MRSA and those with negative colonization swabs) will be re-evaluated in six month intervals ($+/- 2$ months) until the end of the study. Patients found to be positive at these subsequent 6 month intervals, will be randomized again, treated and followed as described above. During the last study visit (at the 2-year time period), patients will have swabs, but not undergo randomization. Hence, every 6 months, patients positive during that visit for MRSA colonization will be re-randomized in a 1:1 double-blinded fashion to mupirocin (Bactroban®) nasal ointment twice daily for seven days plus hexachlorophene (pHisoHex®) washes with showering once daily for seven days or to a placebo nasal ointment (white petroleum) and a placebo body soap with no antimicrobial activity for seven days. Repeat randomization will occur every 6 months for those carrying MRSA. For example, some patients initially randomized to receive Bactroban® and pHisoHex®, may later be randomized to the placebo arm, and vice versa.

Begin at the top of diagram again every 6 months ($+/- 2$ months). If patient is found to be positive on swabs, they are re-randomized to one of the two treatment groups for every 6-month positive swab.

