6.10 Termination

A subject's participation will be terminated if one of the following occurs:

- a. Subject voluntarily withdraws
- b. Subject fails to comply with study procedures
- c. Decision in the best interest of the patient
- d. Patient is no longer eligible for care at the military HIV clinics
- e. Patient becomes pregnant or decides to become pregnant during the two-year study period

- f. The patient begins employment as a healthcare worker with direct patient contact

A subject who develops a rash or significant adverse event due to study medication will be discontinued from treatment but will be encouraged to continue to undergo follow up including study visits for completing questionnaires and swabs for MRSA colonization every 6 months (+/- 2 months) until study completion; the patient will not be randomized to one of the treatment arms if he/she is found to be positive again for MRSA colonization. The subject may be withdrawn from the study if it is felt by the clinical investigators that the subject is at an undue risk from further participation.

The subject will require a termination visit if withdrawn from the study. If a subject's participation in this study is terminated, they will be offered medical standard of care and a medical evaluation, to include clinical laboratory studies as needed. The investigator will complete the Completion/Discontinuation CRF.

VII. STATISTICAL ANALYSES

There are four primary questions to be answered to address this study's primary objective. These, and an analysis designed to answer the question, follow.

- (1) What is the hexachlorophene/mupirocin treatment effect to clear MRSA colonization compared to placebo? We will also examine if these decolonization procedures are effective at reducing MRSA infections and skin/soft tissue infections compared to placebo. We propose to pool the data at 6, 12, 18, and 24 months as if they were independent and conduct a chi-square or Fisher's exact test of contingency. These analyses will be conducted for colonization and infection separately. The proposed pooling of this study design assumes that there is no persistent or repeated-treatment effect and that there is no patient-to-patient difference in susceptibility. These effects will be investigated in the following questions.

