- (2) Is the treatment effect different for repeat administrations of hexachlorophene/mupirocin? The rate of MRSA positive versus negative for recolonization reoccurrence through the sequence 1 versus 2 versus 3 versus 4 treatments will be assessed by a test of trend.
- (3) Is there a persistent or repeated-treatment effect? The overall rates of MRSA recolonization at 6, 12, 18, and 24 months will be assessed by a test of trend.
- (4) Is there an individual propensity for susceptibility and what are the treatment differences between placebo and hexachlorophene/mupirocin in terms of length of time for being negative for MRSA colonization on repeated testing? A Kaplan-Meier long-rank test will be conducted on three groups: initially negative, initially positive treated with hexachlorophene/mupirocin, and initially positive treated with placebo, where survival is defined as not having acquired MRSA.

For the secondary objectives, part (a) will be assessments of the rates in which prevalence is defined as the number of patients colonized with MRSA at the beginning of

the study divided by the total population studied, and the incidence as the number of new infections per calendar time divided by the total population studied. For objective (b) examining for predictors of MRSA, we will create a multivariate logistic regression model and use a backward stepwise approach. For part (c), to evaluate if there is a significant change in the CD4 count and/or viral load pre- versus during a MRSA infection we will utilize a 1-way ANOVA. We will also compare pre-MRSA infection with after MRSA resolution as well as the counts during the infection with those after resolution. Finally, objective (d) will be a descriptive analysis of the molecular and microbiologic characteristics of the isolates. The main statistical data from the retrospective chart review study of HIV patients at NMCSD will be presented by descriptive analyses. We will compare demographics and HIV clinical data between those with and without MRSA using rank sum tests and Fisher's exact tests depending on the variable characteristics (categorical or continuous). A multivariate logistic regression model for predictors of MRSA will then be developed using a backward stepwise approach using Stata software.

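### Questions (2) and (3) ask about a treatment effect but test only trends in MRSA-positive rates with no placebo contrast, so case mix or natural clearance can pass for waning or persistence

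*Combined protocol and SAP*

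**What the plan says.** Section VII opens: "There are four primary questions to be answered to address this study's primary objective". Question (1) pools all 6-monthly results as independent. Among its stated assumptions is that "there is no patient-to-patient difference in susceptibility", and it adds: "These effects will be investigated in the following questions".

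Question (2) then asks whether the effect of hexachlorophene/mupirocin differs on repeat administration. Its analysis, a trend test, is: "The rate of MRSA positive versus negative for recolonization reoccurrence through the sequence 1 versus 2 versus 3 versus 4 treatments will be assessed". Question (3) asks about a persistent or repeated-treatment effect. Its analysis is: "The overall rates of MRSA recolonization at 6, 12, 18, and 24 months will be assessed by a test of trend". Neither names a placebo comparison, an arm-by-course term or a patient term. Question (2) does not say whether it counts active courses or all randomizations, and question (3) gives no denominator.

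Section 6.3 sets who gets a course. First: "Patients found to have a positive culture for MRSA during the study period from the colonization swabs will be randomized". Then: "Patients found to be positive at these subsequent 6 month intervals, will be randomized again", with the arm redrawn 1:1 each time. Finally: "During the last study visit (at the 2-year time period), patients will have swabs, but not undergo randomization". Scheduled courses therefore fall at months 0, 6, 12 and 18, four at most. Section 6.3 also provides for courses at infection visits, under the most recent assignment or as a first randomization.

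The sample-size text in Section VII recognizes that repeat carriers may differ from first-time carriers, also in response, and adds an analysis of first randomizations only.

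**The concern.** A treatment effect is a comparison of active with placebo. A trend in positive rates over course number is not, and here course number depends on earlier outcome, because a patient reaches a second scheduled course only by testing positive again. If some carriers are more persistent than others, they make up a growing share of later courses, and the positive rate climbs even if the treatment works equally well every time.

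Question (3) has a similar gap. An overall trend by month can come from carriers clearing naturally, in both arms alike.

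At stake is a report, under a primary-question label, of lost effect on repeat use or of a lasting effect, when the cause is case mix or natural clearance.

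**Working it through.** **Inputs.** From Section VII: 85% of placebo and 7–39% (mean 23%) of treated carriers remain colonized; 10% of participants colonized; 1:1 allocation; 50–55 randomized (52 used below). The plan gives no figure for question (2), so its sample-size table was reproduced first to confirm the rates. For 85% v 23%, two-sided 0.05, 80% power, p̄ = 0.54:

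- n = [1.96√(2×0.54×0.46) + 0.842√(0.85×0.15 + 0.23×0.77)]² / 0.62² = 8.9
- with continuity correction, (8.9/4)[1 + √(1 + 4/(8.9×0.62))]² = 11.9, so 12 carriers per arm
- 12/0.10 = 120 per group, 240 in total, as printed. The other rows give 8 and 21 carriers per arm, hence 160 and 420, also as printed.

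**Mechanism for question (2), by hand (assumed case mix).** Let 30% of carriers be persistent, with 10 times the odds of staying positive. Matching 23% and 85% overall gives:

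| | Transient | Persistent |
|---|---|---|
| Active | 0.101 | 0.530 |
| Placebo | 0.796 | 0.975 |

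The treatment odds ratio is about 35 within each type and does not change with course.

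- First active course: 0.7×0.101 + 0.3×0.530 = 0.23.
- Persistent share among those still positive: 0.3×0.530/0.23 = 0.69.
- Given active again: 0.31×0.101 + 0.69×0.530 = 0.40.
- Given placebo instead: 0.31×0.796 + 0.69×0.975 = 0.92.

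The active rate rises from 23% to 40% with no waning. The placebo-to-active odds ratio barely moves: (0.85/0.15)/(0.23/0.77) = 19 for the first course, (0.92/0.08)/(0.40/0.60) = 17 for the second. A concurrent placebo contrast removes most of the artefact.

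**Simulation of question (2), no waning.** Assumptions: 52 carriers; 85% v 23% positive at the next 6-month visit (the plan does not tie these rates to 6 months); normal patient effect on the logit scale; 10% re-acquisition; 1:1 re-randomization of positives; Cochran-Armitage trend, two-sided 0.05. Infection-visit courses were not simulated. Share of trials with a significant trend:

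| Counting | SD 0 | SD 0.5 | SD 1 | SD 2 |
|---|---|---|---|---|
| Active courses, all positive at baseline | 4–5% | 5–7% | 11–14% | 32–44% |
| Active courses, staggered first positives | 4% | – | 9–11% | 28–35% |
| Arms pooled | 5–6% | – | 7–9% | 17–26% |

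With the active rate at 7% or 39%, the active-course figures are 8–14% at SD 1 and 19–42% at SD 2. At SD 1–2 at least 95% of rejections point toward waning. About 40–44, 7–10, 1–2 and under 0.3 patients reach active courses 1 to 4. To read the SDs: at SD 1 the middle 80% of patients have a 68–97% chance of staying positive on placebo; at SD 2, 55–99.5%. A different model (30% persistent carriers, 53 randomized, active rate 23–39%) gives false trends of 8–9%, 20–23% and 46–57% at odds ratios 4, 10 and 30.

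**Question (3), by hand, no treatment effect.** Let every patient stay positive with chance 0.85 and re-acquire with chance 0.10. Counting all first-randomized patients:

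- month 6: 0.85
- month 12: 0.85×0.85 + 0.10×0.15 = 0.74
- month 18: 0.85×0.7375 + 0.10×0.2625 = 0.65
- month 24: 0.85×0.653 + 0.10×0.347 = 0.59

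That is a clear downward trend with no treatment effect. Counting only patients randomized at the preceding visit, the rate is 0.85 every time. In simulation the first denominator gives a significant trend in 44–92% of trials with baseline entry, 17–49% with staggered entry, and 4–98% over re-acquisition of 50% to 5%. The second gives about 5–9% at SD 0–1 and 18–27% at SD 2.

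**The case against.** The strongest reply is that the trends are there to check question (1)'s pooling, as Section VII says, and for that they work: a trend caused by patient differences is a proper warning against pooling. The plan also knows that patients differ. Question (4) asks about individual propensity and compares placebo with active treatment, and the first-randomization analysis avoids repeat courses. This stands, and it rules out two stronger readings: that the plan ignores patient differences, and that it has no placebo comparison. It does not close the gap. Section VII also calls these primary questions and offers each trend as the analysis that answers its question. Question (4) groups by initial status, not course number, and the first-randomization analysis drops the repeat courses.

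Second, the size is uncertain. The documents give no patient SD; at SD 0.5 the false-trend rate is close to nominal, and pooling the arms lowers it. A permutation trend test gives 7–10% at SD 1 and 24–39% at SD 2. A reader might infer that false waning is likely, or take 44% as the expected rate. That figure needs SD 2, an upper scenario, together with active-only counting, baseline entry and re-acquisition that shares the patient effect. The sample-size text puts the 10% colonization rate over the study period, which fits staggered entry better.

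Third, the replacement test is weak. That also stands; its cost is given with the fix.

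**Conclusion.** The concern holds as a point about what the stated analyses can answer. Neither trend, as written, answers its question about a treatment effect. How often question (2) would mislead depends on carrier heterogeneity that the documents raise but do not quantify: about 5–7% of trials at SD 0.5, 9–14% at SD 1 and 28–44% at SD 2 counting active courses, and 7–9% and 17–26% at SD 1 and 2 with arms pooled. Apart from the active rates of 7% and 39% tried above, these rest on 85% v 23% at 6 months and a constant within-patient odds ratio.

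For question (3) the risk is large only if all first-randomized patients are counted; with the preceding-visit denominator it is small at SD 0–1. A reader might infer that the question (3) trend is invalid under any denominator, or that the first-randomization comparison is also compromised. The figures do not support the first, and nothing here touches the second. The change should be made, since both arms are already re-randomized concurrently and no new data are needed.

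**What to change.** **Question (2).** Keep the trend only as a descriptive check on pooling, not to be read as waning. Tabulate positive rates by arm and number of earlier active courses (0 v 1+). As an exploratory analysis, test arm by earlier active courses using both arms, with the handling of within-patient correlation prespecified, for example patient-clustered standard errors. A random intercept is not required: at this size the interaction's false-positive rate is 7–8%, 6–7% and 2–4% at SD 0, 1 and 2 with it, and 7%, 6–8% and 2–3% without. Clustered errors, tried on arm by randomization number with 53 randomized and 30% persistent carriers at odds ratios 10 to 30, gave 6–8%, against 20–57% for the trend. State how every infection-visit course under Section 6.3, including first randomizations there, enters the record, the count of earlier active courses and the next 6-month outcome.

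**Question (3).** Do not read the overall trend as persistence. Compare colonization by first randomized assignment 12 months after first randomization, with a confidence interval, as exploratory; show 18 and 24 months descriptively. Time must run from first randomization because patients can enter at different visits. Note that later re-randomization dilutes the contrast.

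**Cost.** Wording only, but with real statistical losses:

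- Interaction power for complete loss of effect is about 58–60%, 46–53% and 22–41% at SD 0, 1 and 2 (48–51%, 37–42% and 16–28% with staggered entry); for half loss, 22%, 15–20% and 9–16%.
- If patients do not differ, the active-course trend given up as an inferential test has 98–99% power for complete loss (92% with staggered entry).
- The question (3) contrast is about 26–29 points at 12 months, with a 95% half-width of 22–25 points (about 27 with staggered entry). It falls to 12–14 and 5–7 points at 18 and 24 months. With baseline entry, about 70% of first-placebo patients later receive an active course.

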The trial will be a randomized, double-blinded study. Patients found to have a positive culture for MRSA colonization will be randomized in a 1:1 fashion to mupirocin (Bactroban®) nasal ointment plus hexachlorophene (pHisoHex®) soap for seven days or to a placebo nasal ointment (white petroleum) and a placebo body soap with no antimicrobial activity for seven days; since there is no standard therapy recommended in the guidelines for MRSA management for MRSA colonization, patients in the latter arm will receive placebos with no specific antimicrobial activity. In this design, we will ascertain if treatment for MRSA decolonization of this patient population is warranted or not. After completion of these topical medications, patients will complete a questionnaire to ascertain their adherence to these medications. Patients found to be colonized with MRSA and who reside locally (within driving distance) to the medical treatment facility will have repeat swabs (five swabs from sites listed above every four weeks (+/- 7 days) after any positive colonization cultures over the subsequent six month time period. These cultures will assist in determining if the decolonization medications were successful at eradicating the carriage of MRSA. Patients will receive one treatment course of either mupirocin (Bactroban®) nasal ointment plus hexachlorophene (pHisoHex®) soap for seven days or a placebo nasal ointment (white petroleum) and a placebo body soap with no antimicrobial activity for seven days. Patients who are initially found to be negative for MRSA on screening swabs will be re-evaluated in six months (+/- 2 months).

Patients who develop a soft tissue infection or any infection thought to be secondary to MRSA will be evaluated in the HIV clinic and will undergo wound cultures and repeated screening for MRSA colonization. CD4 counts and an HIV viral load will be obtained at the time of infection. Patient questionnaires and source documents will be completed for patients experiencing a soft tissue infection or MRSA infection.

Cultures (from colonization sampling and wound cultures) which are positive for MRSA or MSSA at the local medical treatment facilities laboratories will be sent to the San Antonio Military Medical Center (SAMMC) laboratory for confirmation of MRSA, antibiotic susceptibility testing, and molecular analysis.

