Patients experiencing an infection will be offered decolonization medications based on their most recent randomization assignment; those previously randomized will be maintained in their group, while those experiencing a soft tissue infection and having a positive colonization culture for the first time will be randomized to either mupirocin (Bactroban®) nasal ointment twice daily for seven days and hexachlorophene (pHisoHex®) washes with showering once daily for seven days or to a placebo nasal ointment (white petroleum) and a placebo soap with no antimicrobial activity for seven days. Patients with a positive soft tissue culture but no positive swabs from the nares, throat, groin, axilla, or perirectal areas, will not be randomized. If the primary clinician caring for a patient who experienced a MRSA infection desires to decolonize a patient regardless of the patient's randomization group, this is permitted, but must be documented and these participants will be removed from the "placebo group" for the analysis.

All cultures (from colonization sampling, wound and blood cultures) which are positive for MRSA or MSSA at the local medical treatment facilities laboratories will be preserved by freezing the isolates at -70 degrees C; these samples will be batched (isolates will be held at the primary facility and sent on a periodic basis) and sent overnight with dry ice to the NMCSD. This site will collect the specimens and send them to the laboratory at SAMMC which will perform testing on the isolates for confirmation of MRSA, antibiotic susceptibility testing (including mupirocin), and molecular analysis (to include multilocus sequence testing, PVL PCR, and other virulence factors). Some local laboratories (e.g. NMCSD) are also performing susceptibility testing on the isolates; this information will be collected if available. SAMMC will also repeat all susceptibility testing on all isolates at their facility. All samples sent to the laboratory at SAMMC will be labeled only with a PIN number of the patient. The staff at the SAMMC laboratory will not have access to personal identifiers and will have no way of linking their results to a patient name. Results

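### Question (4) asks how the arms differ in time MRSA-negative, but the only test it names is a three-group log-rank test that includes a group not randomized at baseline, and its p-value cannot be read as a treatment effect

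*Combined protocol and SAP*

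**What the plan says.** Section VII opens its list of analyses with "There are four primary questions to be answered to address this study's primary objective". Question (4) has two halves. The first is whether patients differ in susceptibility. The second is "what are the treatment differences between placebo and hexachlorophene/mupirocin in terms of length of time for being negative for MRSA colonization".

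The only analysis given for both halves is this: "A Kaplan-Meier long-rank test will be conducted on three groups: initially negative, initially positive treated with hexachlorophene/mupirocin, and initially positive treated with placebo". (The test meant is the log-rank.) The event is fixed only by a closing clause, "where survival is defined as not having acquired MRSA". No pairwise contrast, hazard ratio or follow-up test is stated.

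The initially negative group has a purpose. Question (1) pools visits on the assumption that "there is no patient-to-patient difference in susceptibility. These effects will be investigated in the following questions", and question (4) is where susceptibility is taken up.

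Only MRSA-positive patients are randomized. Under section 5.1, "Patients who are initially found to be negative for MRSA on screening swabs will be re-evaluated in six months". Some of them may be randomized later, at a six-monthly visit before month 24 (section 6.3) or at an infection visit, where "those experiencing a soft tissue infection and having a positive colonization culture for the first time will be randomized".

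**The concern.** A three-group log-rank test has one null hypothesis: all three curves are equal. If carriers turn positive again more often than non-carriers acquire MRSA, that null is false even when the two arms behave identically. A small p-value then answers the propensity half and says nothing about treatment.

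This matters because question (4) is the only one of the four that asks how long patients stay negative, and it is listed as addressing the primary objective. No active versus placebo time-to-event contrast is stated elsewhere.

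Two definitions are also open.

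- **Event.** Not having acquired MRSA has no clear meaning for someone who is positive at time zero.
- **Initially.** If it means at screening, patients first randomized at months 6–18 or at an infection visit stay in the initially negative group, and their assigned arm is lost to this comparison.

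**Working it through.** **Plan figures.** The plan states no sample size, event count or power for question (4). The nearest figures are in the colonization table of section VII, which uses 85% still colonized on placebo versus 7%, 23% or 39% on active. They reproduce from the continuity-corrected two-proportion formula (two-sided alpha 0.05, power 0.80), divided by 10% colonized. For 85% versus 39%, with mean 0.62 and difference 0.46:

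- n₀ = [1.96·√(2·0.62·0.38) + 0.842·√(0.85·0.15 + 0.39·0.61)]² / 0.46² = 16.2
- n = (n₀/4)·[1 + √(1 + 4/(n₀·0.46))]² = 20.4, so 21 per arm, and 21/0.10 = 210

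The other two rows give 8 and 12 per arm, hence 80 and 120. The 85% and 7–39% can therefore be used as the plan's own rates.

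**Group sizes.** Of 500 followed, 10% is 50, or 25 per arm, which leaves 450. Section 5.2 instead expects 38 per arm of 550, which leaves 474.

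**Method.** Swabs are at 6, 12, 18 and 24 months, and the event is the first positive. At each visit, O − E is summed for each group, with variance D(n − D)/(n − 1) times the usual group-share term. The statistic is referred to chi-square on 2 df (three groups) or 1 df (randomized arms only), alpha 0.05, with 2,000 to 20,000 trials per scenario. The documents give no six-monthly rates for carriers or initial negatives, so the rates below are assumptions.

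**Three-group test, 450/25/25:**

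| Carriers / negatives per visit | Arms identical: three-group rejects | Arms identical: two-arm rejects | Active carriers at negatives' rate: three-group rejects | Same: two-arm rejects |
|---|---|---|---|---|
| 15% / 10% | 43–44% | 5% | 26–27% | 17% |
| 10% / 5% | 68–69% | 5% | 44% | 25% |
| 10% / 4% | 86% | 5% | 61–62% | 35% |
| 10% / 3% | 96–97% | 5% | 79–80% | 50% |
| all equal | 5% | 5% | – | – |

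With 474/38/38 and identical arms, the four unequal-rate rows become 57%, 82%, 95% and 99%.

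The reason shows in the 10%/5% row. By 24 months 1 − 0.90⁴ = 34.4% of carriers and 1 − 0.95⁴ = 18.5% of negatives have turned positive. Fifty carriers give about 17 events, where the negatives' rate would give about 9, with no treatment effect.

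**At the plan's rates** (placebo 85% at the first visit; 5% assumed at later visits and in negatives), the three-group test rejects in 100% of trials with no effect, and in 100% with active at 39%, 23% or 7%. It does not discriminate at all.

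**Power of a two-arm test, 25 per arm:**

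- 85% versus 39%: about 87% (later visits 10% in both arms) to 99% (first-visit rates continue).
- 85% versus 23% or 7%: about 98–100%.
- 60% on placebo, later visits 5%: about 28% against 39% and about 66% against 23%.
- Carrier rates of only 10–15% per visit: 17–50% (last column of the table).
- If half of the 50 were first randomized after baseline and left out, 12 per arm would remain, with 58–82% for 85% versus 39%.

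At 85% versus 7–39%, about 78–93% of the log-rank variance comes from the first six-monthly visit.

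**The case against.** The strongest reply is that the plan is under-specified rather than wrong. It names the contrast in the question, keeps the arms as separate groups, and does not say that a single global p-value will be the only result. That stands. A reader might infer that pairwise tests are ruled out or that the arms will never be compared on time negative; the text does not say so. What remains is that the contrast, event and time origin would be chosen after the data are seen.

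Second, the rejection rates of 43–97% might be read as false-positive rates. They are not errors for the propensity half, since carriers truly differ from negatives in those scenarios. They become errors only if read as treatment effects.

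Third, the table might suggest that the test moves the wrong way, rejecting less often when treatment works. That occurs only at the low assumed rates. At the plan's own rates the test is saturated at 100% and does not reverse.

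Fourth, later-randomized patients need not be lost. Section VII defines unique randomizations by a subject's initial randomization, so initially positive could mean positive at first randomization. The wording allows both readings.

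Finally, question (1) and the unique-randomization analysis already compare the arms directly. That limits the harm but does not answer the time question.

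**Conclusion.** The concern holds in a limited form. The one test named for question (4) can address propensity but cannot be read as a treatment effect on time negative. With identical arms it rejects in about 43–97% of trials under the assumed rates, and in 100% at the plan's 85% (5% assumed elsewhere), against about 5% for a two-arm test. The percentages rest on assumed six-monthly rates and on treating all 50 randomized patients as initially positive with four visits ahead of them. The direction does not: any carrier versus non-carrier difference can reject the three-group null.

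A reader might go further and conclude that the trial lacks a valid comparison of the arms or that its main analysis is compromised. The documents do not support that, because the arms are compared as proportions elsewhere. The damage is confined to the time-to-event claim. Severity is minor to should-fix.

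**What to change.** Split question (4) in the analysis section.

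1. **Treatment half.** Name a two-arm log-rank test of active versus placebo in randomized patients only, by first assignment, with time zero at first randomization whenever it occurs. Define the event as the first MRSA-positive swab after treatment, on a swab schedule common to both arms, and state that it combines persistence and recolonization. The six-monthly visits are a schedule that everyone shares. The 28-day swabs in local patients could also serve, since living locally does not depend on assignment.
2. **Propensity half.** Report initially positive versus initially negative patients separately, labelled as non-randomized, and say what initially means.

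Section 6.3 says of decolonization outside assignment that "this is permitted, but must be documented and these participants will be removed from the" placebo group. How that rule meets analysis by first assignment is a separate population question; one sentence should say which applies here.

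The cost is a few sentences and no new data. The downside is that only about 50–76 patients contribute (25 to 38 per arm). Power is good at the plan's rates but falls to about 28–66% if only 60% on placebo are positive at six months (versus 39–23% on active, later rate 5% assumed), and to 17–50% if carrier rates are only 10–15% per visit. At the plan's rates the first six-monthly visit dominates, so the test will add only modestly to the unique-randomization analysis.
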